**Evaluation of Web-Based CBT for Women Veterans with PTSD**

**NCT02917447**

**April 6, 2020**

## STUDY PROTOCOL WITH STATISTICAL ANALYSIS PLAN

**Recruitment.** Women Veterans with PTSD (target  $N = 100$ ) were recruited for this RCT. Veterans who met the following criteria were identified by national VA electronic medical records: (1) age 18 or older, (2) female, (3) Veteran, (4) lives in a state with a Pacific or Mountain time zone (i.e., New Mexico, Arizona, Montana, Wyoming, Colorado, Utah, Washington, Idaho, Oregon, California, Nevada), (5) has an ICD code for PTSD or a positive VA mandated PTSD screen, (6) no mental health stop code (reflecting VA-based visits) in the last two months, and (7) not on the high risk list of imminent danger to self or others. Approximately 30,000 women met these criteria. Because the study aimed to enroll women who were not actively engaged in current mental health care (defined as prior two months), this criterion was applied when identifying potential participants via medical records. Randomly selected women were mailed letters approximately every other week in batches of 100-200 letters inviting them to potentially participate in the study. The invitation letter included an overview of the study and directed women to contact the study office for more information. Each individual may have received up to two invitation letters and up to three follow-up phone calls to assess her interest and eligibility.

Inclusion criteria for the RCT included: (1) age 18 or older, (2) female, (3) Veteran, (4) current PTSD as assessed by the CAPS-5 interview, (5) reports routine access to computer and Internet, and (6) provides written research informed consent using IRB-approved form, including willingness to be audio-taped during the eligibility interview and study coach calls, willingness to be left voice messages, and availability of at least one collateral contact.

Exclusion criteria included: (1) on VA “high risk” list for imminent danger to self or others, (2) currently at imminent danger of harm to self, according to the M.I.N.I. International

Neuropsychiatric Interview – Suicidality instrument, (3) actively engaged in individual therapy in the past two months, and/or receiving couple's or group therapy in the past two months if that therapy focuses on PTSD at a frequency of once per month or more, (4) scheduled to receive a future individual therapy appointment, or a future couples' or group therapy appointment if that therapy focuses on PTSD, at a frequency of once per month or more, (5) moderate or severe alcohol use disorder or any non-alcohol substance use disorder in the past year excluding mild cannabis or any nicotine abuse, (6) acute psychosis, psychotic episode, or psychotic disorder diagnosis within the past year, (7) homicidality, and (8) unstable administration schedule or dosing of any antidepressant, anxiolytic, or sedative-hypnotic (i.e., will exclude for any related medication changes in the four weeks prior to the eligibility interview). Furthermore, women who participated in earlier phases of the research (qualitative interviews and the pilot study) were not included. These criteria are consistent with PTSD RCTs and PTSD telehealth research (Morland et al., 2009; Schnurr et al., 2003).

**Study procedure.** The study involved three assessment phases: eligibility, baseline, and follow-up (post-treatment and 3- and 6-month follow-ups). The eligibility interview was conducted by a study assessor via telephone. Baseline and follow-up assessments were conducted online. Participants were randomized to condition following the baseline assessment.

***Eligibility screener and interview.*** When interested women Veterans contacted the study office, study staff conducted a pre-consent eligibility screening, which consisted of questions corresponding to inclusion/exclusion criteria. The purpose of the pre-consent eligibility screening was to quickly determine which candidates are most likely to qualify, thus eliminating the need to conduct consent and full eligibility interviews for all potential participants. If patients were found to be eligible following the pre-consent eligibility screening, study staff reviewed the

consent, answered any questions, and mailed the consent form to the participant to obtain written consent. The full eligibility interview was scheduled at this time and conducted only when written, signed consent had been received in the study office. The full eligibility interview included a collection of demographic information as well as the Mini International Neuropsychiatric Interview (MINI) to assess substance use disorders (Lecubrier et al., 1997) and the CAPS-5 (Weathers et al., 2013). PTSD diagnosis on the gold-standard CAPS was required for study eligibility. The staff member who conducted the eligibility interview in the role of study assessor did not serve as the participant's study coach to avoid potential bias during the assessment. If the interval between the eligibility interview and baseline assessments was longer than four weeks, we required re-administration of CAPS via telephone to ensure PTSD status.

***Baseline and follow-up assessments.*** The baseline and follow-up assessments (at post-treatment and 3- and 6-month follow-ups) consisted of an online survey hosted by SurveyMonkey (SurveyMonkey Inc., Palo Alto, CA). Information collected during the online baseline assessment served as a baseline from which to evaluate the efficacy of the study intervention on the primary outcome (PTSD symptom severity) and secondary outcomes (depression and quality of life). Information about concurrent treatment that might moderate the efficacy of the study intervention ("co-therapies") was also gathered at the baseline assessment (e.g., mental health specialty visits, PTSD-related pharmacotherapy use, and chaplain or similar community support resources) and throughout the course of the study. Following the baseline assessment, patients were randomly assigned to one of the study conditions. Participants received \$25 for the baseline assessment, \$30 for each of the three follow-up assessments, and a \$35 bonus for completing all assessments (for a total maximum of \$150).

**Randomization.** We used the Sealed Envelope™ program (Sealed Envelope Ltd., 2016) to generate a randomization table to condition (1:1 allocation ratio) using a permuted block design with block sizes of two and four to maximize the likelihood of a balanced sample size across arms (Schulz & Grimes, 2002), and stratifying by rural status to facilitate exploratory analyses of the impact of this variable on trial outcomes and to maximize the likelihood of balance across arms on this potential characteristic (Kernan et al., 1999). We defined rural status as living more than 40 miles away from the closest VA medical facility, in line with eligibility criteria used by the Veterans Access, Choice, and Accountability Act and shown to be a marker indicating decreased likelihood of receiving psychotherapy (Pfeiffer et al., 2010).

**DESTRESS-WV intervention.** For the DESTRESS-WV condition, the initial telephone session with the study coach served to 1) provide brief psychoeducation regarding PTSD; 2) complete a safety plan that is individualized to the patient for times when she is distressed; 3) introduce the intervention model, the study coach role, and the participant's role; 4) introduce the patient to the website's structure; and 5) problem-solve any obstacles to using the website. Participants were asked to log on the website twice a week each week for eight weeks and complete different homework activities. Nonetheless, up to 12 weeks of access was provided. The coach called the participants once a week at an agreed upon time while they were completing the program to monitor symptoms and safety, review progress through the website, provide encouragement, review a particular skill or strategy when applicable, review barriers to treatment compliance, and address barriers to treatment (target call time is 15 minutes). The coach had access to a back-end of the DESTRESS-WV website where she monitored participants' progress, and this was monitored weekly between every study coach call.

Before completing each session, participants were encouraged to plan 30-60 minutes free from interruption, during which they can review that session's content. Sessions covered basic coping skills (deep breathing, progressive muscle relaxation, and reaching out for support); cognitive strategies to identify and challenge unhelpful thoughts; in-vivo exposures; writing about stressful, daily life events; and writing about and processing a traumatic experience. Sessions could only be accessed at a minimum of 24 hours apart to promote appropriate pacing and provide opportunity to complete homework assignments.

***DESTRESS-WV homework.*** After the first session, each time participants logged on to the DESTRESS-WV site, they were prompted to enter responses from the previous session's homework assignment. Broken up into units, these assignments promoted stress-reduction skills, self-monitoring, application of stress management techniques to each in vivo exercise, processing and coping with a particularly salient or intense traumatic memory as well as significant current-day stressors, and relapse prevention. Participants were required to complete a given homework assignment before proceeding to the next session, otherwise the sessions did not progress. Participants were also reminded of the study coach's phone number and could call the coach at any time with questions or concerns. Study coach voicemails were monitored daily during regular business hours.

**Phone monitoring only.** The purpose of the phone monitoring condition was to assess participants' safety and symptoms, similar to the DESTRESS-WV condition, while providing general support in a safe atmosphere where participants were actively being listened to and empathized with by the coach. The aim of using this approach was to provide an alternative and to control for nonspecific therapeutic factors, including regular supportive contact with study staff.

The initial telephone session served to: (1) provide brief psychoeducation regarding PTSD; (2) complete a safety plan that is individualized to the participant for times when she is distressed; and (3) introduce the study coach and the participant's roles. Participants were expected to attend calls weekly and, in addition to answering questions regarding their weekly symptoms, were encouraged to discuss any issues from the week they would like. The coach used active listening and reflective statements but did not actively encourage the use of CBT strategies, as in the DESTRESS-WV condition. Calls were expected to last an average of 15 minutes, similar to the length of calls in the DESTRESS-WV condition.

**Outcome measures.** Baseline, post-treatment, and 3- and 6-month surveys all assessed outcome measures and were conducted online, thus eliminating the need for a blind assessor.

**Primary outcome.** The PTSD Symptom-Checklist –Version 5 (PCL-5) was used to assess symptoms of PTSD at baseline and follow-up assessments (Weathers et al., 2013). This is a 20-item, self-report instrument that assesses the presence and severity of DSM-V PTSD symptoms in the last month. It can be summed for a total severity score, ranging from 0-80. PCL-5 test scores have demonstrated good internal consistency ( $\alpha = .96$ ), test-retest reliability ( $r = .84$ ), and convergent and discriminant validity with samples of Veterans (Bovin et al., 2015).

**Secondary outcomes.** The Patient Health Questionnaire (PHQ) is a brief self-report assessment of common mental disorders and was used to assess symptoms of depression (PHQ-8; Kroenke et al., 2009). The eight items specifically correspond to symptom-based diagnostic criteria in DSM-IV, and demonstrate good validity, reliability, and sensitivity to change (Kroenke & Spitzer, 2002). The Quality of Life Enjoyment and Satisfaction Questionnaire – Short Form (Q-LES-Q-SF) was used to assess quality of life (Endicott et al., 1993). It consists of

16 items and has been shown to have good internal consistency, test-retest reliability, validity, and sensitivity in clinical settings (Stevanovic, 2011).

***Process outcomes.*** Feasibility of DESTRESS-WV was examined by completion of intervention sessions and retention of participants through the duration of the intervention. For the DESTRESS-WV treatment arm, we defined a “treatment completer” as someone who completed at least nine of the 16 intervention sessions, and for the phone monitoring only arm we defined a treatment completer as someone who completes at least five of the nine coaching calls. We hypothesized that no more than 30% of the women in this study will dropout from the study (withdraw or be lost-to-follow-up), similar to overall dropout rates for PTSD trials (Imel et al., 2013). Of the women who do not dropout, we hypothesized that at least 70% will be treatment completers as per the above definitions, similar to participation rates found by Engel et al. (2015).

Acceptability was evaluated by participants in both study groups using the Client Satisfaction Questionnaire-8 (CSQ-8; Larsen et al., 1979), an 8-item measure on a 4-point Likert scale that assesses general satisfaction with treatment. For example, participants rate the quality of the service they received, the extent to which the program met their needs, the extent to which they were satisfied with the amount of help received, and whether services helped them deal more effectively with their problems. The measure has good internal consistency, construct validity, and criterion-related validity (Attkisson & Zwick, 1982). An additional item assessed how satisfied participants were with receiving treatment through the phone or Internet (based on assigned condition), from 0 (*not at all*) to 4 (*very much*). Finally, seven items created for the study assessed satisfaction with the study coach, ranging from 0 (*not at all*) to 4 (*very much*). Items included how much the participant liked the coach, how helpful the coach was, and how

much the participant felt the coach listened and understood them. We hypothesized that overall mean satisfaction will be greater than the mid-point of the scale.

**Participant safeguards.** As noted above, during the first phone call with the study coach, participants in both conditions created a personalized safety plan. This included identifying healthy coping strategies that could be done alone (e.g., going for a walk, engaging in a pleasurable activity) as well as identifying individuals in their support network they can call. The safety plan also included the Veterans Crisis Line number and the study coach's contact information.

Participants were carefully monitored for signs of clinical deterioration that may jeopardize their health or warrant removal from the study. During the treatment phase, at each call (nine calls for a total of eight weeks), the study coach assessed PTSD symptoms using an abbreviated PTSD Checklist (PCL) that consisted of seven items (three re-experiencing symptoms, two avoidance symptoms, two hyperarousal symptoms). Participants rated each symptom from 1 (*not at all*) to 5 (*extremely*). If there were an increase of seven or more points on this abbreviated PCL (i.e., 20% of the maximum possible score) from the baseline score (i.e., score on first coach call before initiation of treatment), the study coach discussed with the participant whether it appears that the exacerbation was related to study participation or was likely situational (e.g., life stressors or changes in circumstances often precipitate PTSD exacerbations, as do trauma anniversaries). If it appeared to be the former, the possibility of withdrawing from the treatment aspects of the study were discussed with the participant and PI and a decision reached mutually.

Any patient who became actively suicidal was assessed by the study coach using the study's Safety Protocol. The Safety Protocol assessed and identified whether current risk was

minimal (hopelessness or ideation only), moderate (ideation and plan but no intent), or imminent (ideation, plan and intent). Clear guidelines were offered in accordance with each risk level (e.g., moderate risk entailed providing the participant with the Veterans Crisis line and local resources and recommending follow-up mental health care in 24 hours).

All participants who withdrew from the treatment protocol were given the option of continuing to provide information at the follow-up assessments for intent-to-treat analyses of outcomes. Additionally, participants randomized to DESTRESS-WV were reminded of the study office phone number and the Veterans Crisis Line during each logon. Participants were also reminded of these phone numbers and other resources after each follow-up assessment.

**Power.** This is a pilot RCT designed to provide estimates of feasibility of the treatment approach, dropout rates, acceptability, and initial effect sizes. The study's budget and timeline allows us to plan to randomize 100 participants. For the primary outcome, Litz et al. (2007) observed a differential effect size of 0.41 at 8 weeks ( $n = 33$ ), 0.10 at 3 months ( $n = 24$ ), and 0.95 at 6 months ( $n = 18$ ) when comparing change from baseline in PTSD symptoms for participants randomized to DESTRESS ( $n = 24$ ) versus supportive counseling ( $n = 21$ ), with an overall dropout rate of 27% prior to the end of 8 weeks of therapy. In a second trial of DESTRESS by Engel et al. (2015) where participants were randomized to optimized usual care ( $n = 37$ ) or DESTRESS ( $n = 43$ ), the 6-week effect size was 0.23 ( $n = 64$ ), the 12-week effect size was 0.47 ( $n = 62$ ), and the 18-week effect size was 0.08 ( $n = 66$ ), with an overall dropout rate of 18%.

As noted above, we hypothesized no more than 30% of participants will dropout prior to the end of the study. Thus, with the goal of randomizing 100 participants and assuming a sample size of at least  $n = 35$  participants per group, we have 80% power to detect an effect size of 0.68 using a two-sided Type I error rate of 5%.

Following the recommendation of Bacchetti (2010), Table 1 presents a sensitivity analysis of possible results from this study in terms of 95% confidence intervals for the difference in change from baseline in PCL-5 for the DESTRESS-WV versus the phone monitoring only group. Engel et al. (2015) state that for their study of DESTRESS versus optimized usual care (OUC), for PCL-4 the observed 12-week change from baseline (Mean  $\pm$  SD) was  $12.6 \pm 16.6$  for the DESTRESS group and  $5.7 \pm 12.5$  for the OUC group. In our table the pooled standard deviation of change from baseline varies from 8 to 22, while the possible difference in change from baseline between groups varies from 0 to 14. The numbers in parentheses after the confidence intervals are the effect sizes.

**Table 1.** Sensitivity Analysis of Possible Results for Difference in Change from Baseline Between Groups (95% Confidence Intervals and Effect Sizes)

	Difference = 14	Difference = 7	Difference = 0
SD = 8	[10.2, 17.8] (1.8)	[ 3.2, 10.8] (0.9)	[ -3.8, 3.8] (0)
SD = 15	[ 6.8, 21.2] (0.9)	[-0.2, 14.2] (0.5)	[ -7.2, 7.2] (0)
SD = 22	[ 3.5, 24.5] (0.6)	[-3.5, 17.5] (0.3)	[-10.5, 10.5] (0)

**RCT data analytic strategy.** We used summary statistics (e.g., means, standard deviations, percentages) and graphs (e.g., strip charts, box plots, bar charts, scatter plots) to compare participant demographics at baseline by assigned treatment group (DESTRESS-WV vs. phone monitoring only), and to initially compare outcomes by treatment group. Analyses followed the intent-to-treat principle, so that all participants who had at least a baseline assessment and were randomized were included in the analyses. For descriptive purposes, analyses were conducted to determine group comparability on baseline participant characteristics and potential moderator variables. Because differential attrition can compromise inference about treatment effectiveness, we compared study dropouts versus non-dropouts and treatment non-completers versus treatment completers on demographic and outcome variables. Dropouts

included those who withdrew from the study or were lost-to-follow-up; treatment non-completers may or may not be study dropouts as treatment non-completers were invited to continue participating in study assessments. Treatment completers include those completing nine or more sessions of DESTRESS-WV or, for those in the phone monitoring condition, five of the nine coaching calls.

To account for repeated measures within subjects, we used a linear mixed effects model for the analysis of the primary outcome, PCL-5, with the subject treated as a random effect. We have PCL-5 measures at four times during the course of the study: at baseline, 8 weeks (the first post-treatment assessment), and 3 and 6 months post-treatment. The response (dependent) variable was PCL-5 score, and the predictor (explanatory) variables included treatment group, assessment visit (treated as categorical), and a treatment group by assessment visit interaction term, along with the covariates trauma category and rural status. A significant treatment group by visit interaction term indicates a significant difference in change from baseline between treatment groups. Results include adjusted means, standard errors, and 95% confidence intervals for each group at each time, confidence intervals for change from baseline at each time within each group, confidence intervals for differences in change from baseline between the two groups at each time, p-values, and effect sizes. We also used linear mixed effects models for the two secondary outcomes, depression and quality of life.

Linear mixed effects models easily accommodate missing values. We compared the rate and timing of dropouts between treatment groups, and also baseline demographics and outcome scores between treatment completers and non-completers. If necessary, we will perform sensitivity analyses by using only participants who were treatment completers and using multiple imputation to deal with missing values.

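### The two numeric feasibility benchmarks pool the phone arm with DESTRESS-WV, so if the arms differ, meeting or missing them does not show whether DESTRESS-WV itself reached them

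*Combined protocol and SAP*

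**What the plan says.** All references are to the combined protocol and SAP.

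- **Process outcomes** names the object and the measures: "Feasibility of DESTRESS-WV was examined by completion of intervention sessions and retention of participants through the duration of the intervention".
- It defines completers separately by arm: at least nine of 16 web sessions for DESTRESS-WV, while "for the phone monitoring only arm we defined a treatment completer as someone who completes at least five of the nine coaching calls".
- It then sets two numeric benchmarks. For dropout: "no more than 30% of the women in this study will dropout from the study (withdraw or be lost-to-follow-up". For completion: "Of the women who do not dropout, we hypothesized that at least 70% will be treatment completers as per the above definitions".
- **Power** repeats the dropout figure for the whole trial, "we hypothesized no more than 30% of participants will dropout prior to the end of the study", and derives the evaluable sample from it: "with the goal of randomizing 100 participants and assuming a sample size of at least" 35 per group. It also gives the trial's purpose: "This is a pilot RCT designed to provide estimates of feasibility of the treatment approach, dropout rates, acceptability, and initial effect sizes".
- **Randomization** describes a "randomization table to condition (1:1 allocation ratio", so 100 women means about 50 per arm.
- **RCT data analytic strategy** compares the rate and timing of dropout between the arms. It compares completers with non-completers on baseline and outcome variables. It does not name a comparison of completion between the arms.

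**The concern.** The question concerns one arm, but the yardsticks are set on two. The dropout benchmark refers to all women in the study. The completion benchmark refers to all women who do not drop out, with the phone arm's five-of-nine-calls definition counted alongside the nine-of-16-sessions definition.

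The arms ask for different work. DESTRESS-WV asks for two logins a week for eight weeks, with homework that must be done before the next session opens, in-vivo exposure and trauma writing. The phone arm asks for weekly supportive calls of about 15 minutes. Unequal completion is therefore plausible, although the documents do not show it. If it occurs, strong attendance at calls can lift the pooled rate over 70% while DESTRESS-WV falls short, and weak attendance can pull it under 70% while DESTRESS-WV succeeds.

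The completion benchmark is also conditional on staying in the study. Women who withdraw or are lost leave its denominator, so it does not by itself give the share of women assigned to DESTRESS-WV who complete it.

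Feasibility is the first purpose that the Power section lists, and these are the plan's only numeric targets for retention and completion.

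**Working it through.** **Inputs from the documents.** 100 women randomised 1:1; dropout at most 30%; completion at least 70% of non-dropouts; 35 evaluable per group; 80% power for an effect size of 0.68 at two-sided 5%.

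**The plan's own figure.** 100 × (1 − 0.30) / 2 = 35 per group. Two-sample t-test power at n = 35 per group and effect size 0.68 is 80.1%, so the stated 80% reproduces. The calculation uses the 30% as an all-participant figure, which supports the pooled reading of the dropout benchmark.

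**Assumptions.** The documents give no arm-specific rates. I assume 50 women per arm, with 15 dropouts and 35 retained in each unless stated otherwise.

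**1. Completion counts.** The pooled benchmark needs 0.70 × 70 = 49 completers.

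- If 28 of 35 complete in the phone arm, DESTRESS-WV has 49 − 28 = 21, and 21/35 = 60%.
- If 32 of 35 complete in the phone arm, DESTRESS-WV has 49 − 32 = 17, and 17/35 = 49%.
- Other direction: 25 of 35 (71%) in DESTRESS-WV with 20 of 35 (57%) in the phone arm gives 45/70 = 64%, a pooled miss although DESTRESS-WV is above 70%.

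**2. How often the two readings disagree on completion.** Let D ~ Bin(35, p_D) and P ~ Bin(35, p_P), independent. The pooled benchmark is met if D + P ≥ 49. The within-arm benchmark is met if D ≥ 25 (70% of 35 is 24.5).

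| Assumed true completion, DESTRESS-WV / phone arm | Pooled met | DESTRESS-WV met | Pooled met, DESTRESS-WV missed | DESTRESS-WV met, pooled missed |
|---|---|---|---|---|
| 55% / 85% | 56% | 3.5% | 53% | 0.01% |
| 60% / 80% | 56% | 11% | 45% | 0.2% |
| 70% / 70% | 56% | 51% | 15% | 10% |
| 80% / 60% | 56% | 93% | 0.6% | 37% |
| 85% / 55% | 56% | 99% | 0.03% | 43% |

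All five rows average 70%, and the pooled benchmark cannot tell them apart. With equal arms, disagreement is chance alone: about 25% in total at 70/70 (14.9% plus 10.1%), about 10% at 60/60 and about 7% at 80/80.

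**3. Dropout.** With 20 dropouts in DESTRESS-WV and 10 in the phone arm, the pooled rate is 30/100 = 30%, which meets the benchmark. DESTRESS-WV is at 20/50 = 40%, with 30 women retained against the 35 in the Power section. With D ~ Bin(50, 0.40) and P ~ Bin(50, 0.20), the probability that D + P ≤ 30 while D > 15 is 46%. With both true rates at 30% it is 11%, again chance.

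**4. Effect of conditioning on retention.** In the 17/35 case, completers as a share of all 50 assigned are (17 + k)/50, where k is the number of the 15 dropouts who had already completed nine sessions. For k = 0 to 15 this runs from 34% to 64%.

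**5. Precision lost by looking at one arm (Wilson 95%).**

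| Rate | One arm | Pooled |
|---|---|---|
| Dropout 30% | 19% to 44% (15 of 50) | 22% to 40% (30 of 100) |
| Completion near 70% | 55% to 84% (25 of 35) | 58% to 79% (49 of 70) |

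**The case against.** The case against is substantial, and much of it stands.

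- **The plan already points at the arm.** The opening sentence of Process outcomes makes session completion a feasibility measure for DESTRESS-WV, and only that arm has web sessions. A DESTRESS-WV completion rate can be computed from the separate definitions, and dropout is explicitly compared by arm. A reader might infer that the plan cannot show whether DESTRESS-WV was feasible, or that arm-level data will be missing. The documents do not support that. The gap is narrower: neither numeric benchmark is applied to the arm in question, and no between-arm completion comparison is named.
- **The pooled 30% matches its source.** The plan ties it to overall dropout in PTSD trials, and the two earlier DESTRESS dropout figures in the Power section (27% and 18%) are also overall rates. This stands. It is a reason to keep the pooled figure for power, and to use 30% as a reference value for the arm, not as a validated standard.
- **Nothing hangs on the benchmarks.** They are hypotheses in a pilot meant to give estimates, with no go/no-go rule. This stands and limits the severity.
- **A within-arm pass mark is also unstable.** At a true 70%, at least 25/35 is reached only 51% of the time. This stands, and is why an arm-level rate with its interval is more useful than a relocated pass or fail.
- **The large disagreements are assumed.** Four of the five table rows assume gaps of 20 or 30 points, and all five sit at an average of 70%, where pass or fail is least stable. This stands. Away from 70%, disagreement stays large only if the arms really differ: at 70/90 it is about 48%.

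**Conclusion.** The point holds as a modest one. Read plainly, the dropout and completion benchmarks are pooled, and the Power section confirms this for dropout. If the arms differ, meeting or missing them does not show whether DESTRESS-WV reached 70% retention or 70% completion. The size depends on an arm difference that the documents neither report nor rule out. It is about 45% discordance in one direction at 60/80 and about 37% in the other at 80/60; with equal arms it is chance only. These figures assume 35 women retained per arm and independent binomial outcomes.

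The by-arm dropout comparison partly covers retention. Completion has no equivalent in the analysis section. A reader might go further and infer that the pooled benchmarks will mislead in this trial. That does not follow, because no arm-specific rates are given and no decision rule is attached. Confidence is medium, because the opening sentence of Process outcomes could be read as signalling an arm-specific intent.

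**What to change.** - Base the conclusion on DESTRESS-WV feasibility on that arm's own dropout and completion rates, each with a 95% confidence interval, read against the existing 30% and 70% as reference values.
- Also report DESTRESS-WV completers (at least nine of 16 sessions, whether or not later lost) as a share of all women randomised to that arm, with a 95% confidence interval and no new pass mark.
- Show the phone-arm and pooled rates alongside as context, and keep the pooled 30% for the power calculation.
- If outcomes have already been seen, label the by-arm reading as added later.

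The cost is a few lines of SAP wording and a re-tabulation of data that the trial already collects. The statistical price is the wider one-arm intervals shown in the working.

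### The only numeric trigger for PTSD-symptom worsening, a rise of 7 or more on a 7–35 scale, cannot be met by a woman whose first-call score is 29–35

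*Combined protocol and SAP*

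**What the plan says.** All of this is in the Participant safeguards section of the combined protocol and SAP, unless another section is named.

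- **General duty.** "Participants were carefully monitored for signs of clinical deterioration that may jeopardize their health or warrant removal from the study". No level is attached to this statement.
- **Instrument and timing.** "at each call (nine calls for a total of eight weeks), the study coach assessed PTSD symptoms". The form is a shortened PTSD Checklist with seven items, each rated from 1 to 5.
- **Trigger.** "If there were an increase of seven or more points on this abbreviated PCL", a size explained as "20% of the maximum possible score". The reference is the "score on first coach call before initiation of treatment".
- **Action.** The coach and participant discuss whether the worsening comes from the study or from circumstances. If it seems to come from the study, "the possibility of withdrawing from the treatment aspects of the study were discussed with the participant and PI and a decision reached mutually".
- **Other safeguards.** Both arms have individual safety plans. For suicide risk, "Any patient who became actively suicidal was assessed by the study coach" under a graded Safety Protocol. The DESTRESS-WV intervention and Phone monitoring only sections describe weekly calls that ask about symptoms. The DESTRESS-WV homework section lets participants phone the coach at any time.

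The inclusion criteria, under Recruitment, require current PTSD on the CAPS-5. Neither they nor the exclusion criteria set an upper limit on PTSD severity.

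**The concern.** A fixed change from baseline on a bounded scale stops working once the baseline is closer to the ceiling than the required change. Here that happens among the women with the worst symptoms at the first call, and the text makes no provision for it.

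The effect runs against severity. A woman who moves from 20 to 27 meets the rule. A woman who moves from 29 to 35, the top rating on every item, does not.

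What is lost is a prompt. The 7-point rise does not stop treatment; it obliges the coach to ask whether the worsening is study-related and, if it seems so, brings in the investigator. That question matters most in the DESTRESS-WV arm, whose sessions include in-vivo exposure and writing about trauma. For women who start at 29–35 the rule never raises the question, so it depends on the general monitoring duty, which states no level.

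**Working it through.** **Inputs** (all from Participant safeguards): 7 items; ratings 1 to 5; trigger a rise of at least 7; reference the first-call score; 9 calls.

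**Scale range.** Minimum 7 × 1 = 7; maximum 7 × 5 = 35. Possible totals: 35 − 7 + 1 = 29.

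**The plan's own figure.** 7 / 35 = 0.20. The stated 20% is correct, so this is a ceiling problem and not an arithmetic slip.

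**Reachability.** Largest possible rise = 35 − first-call score. The rule can be met only if this is at least 7, that is, if the first-call score is 28 or lower. The last column is the rise needed if the rule also fired on reaching 35 from a lower start: min(7, 35 − start).

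| First-call score | Mean item rating | Largest possible rise | Current rule reachable? | Rise needed with added clause |
|---|---|---|---|---|
| 27 | 3.86 | 8 | yes | 7 |
| 28 | 4.00 | 7 | only at 35 | 7 |
| 29 | 4.14 | 6 | no | 6 |
| 30 | 4.29 | 5 | no | 5 |
| 31 | 4.43 | 4 | no | 4 |
| 32 | 4.57 | 3 | no | 3 |
| 33 | 4.71 | 2 | no | 2 |
| 34 | 4.86 | 1 | no | 1 |
| 35 | 5.00 | 0 | no | none possible |

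The current rule is unreachable from 7 of 29 scale points. With the added clause this falls to one (35). The added clause changes nothing at 28 or below, because reaching 35 from there is already a rise of at least 7, and there is no jump between 28 and 29 (7, then 6).

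**Is there another PTSD-symptom action level?** The general deterioration statement gives none. The weekly calls collect symptoms without a threshold. The Safety Protocol grades suicide risk, not PTSD symptoms. Safety plans and the coach's phone line set no level. No absolute-score or ceiling rule appears anywhere in the document.

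**How many women?** The document gives no distribution of first-call scores, so 7 of 29 describes the scale and is not a share of participants. Purely as an assumption, a rounded, truncated normal first-call score with mean 20 to 26 and SD 4 to 6 puts between 1.7% (mean 20, SD 4) and 29.9% (mean 26, SD 6) at 29 or above. The share could be negligible or material; the document cannot say which.

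**Added burden.** Nine calls less the baseline call leaves 8, so at most 8 extra discussions per affected woman.

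**The case against.** The strongest reply accepts the arithmetic and disputes the importance.

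- **Women near the ceiling were still monitored.** A coach spoke to them weekly, they could raise any issue, the general duty covers deterioration serious enough for removal, and nothing makes the 7-point rise the only route to discussing withdrawal. This stands, and it limits the point to the loss of a numeric prompt.
- **The number affected is unknown.** This also stands. The arithmetic is certain; the clinical consequence is not.
- **Any change rule on a bounded scale weakens near the top, and a fixed change is a legitimate choice.** True, but that argues for a ceiling provision and does not excuse the lack of one.
- **The added clause is blunt.** From 29 to 33 it fires only when every item is at 5, so a move from 29 to 34 still gives no prompt. From 33 or 34 it can fire on a chance rise of 2 points or 1. For a start of 35 it relies on what the woman reports. These limits are real. They are tolerable because the result is a conversation within a scheduled call, and the clinical team can choose a lower cut.
- **The limit of 8 may be exceeded.** The DESTRESS-WV intervention section allows up to 12 weeks of access, with weekly calls while the program is being completed. The limit rests on the nine calls stated under Process outcomes and Participant safeguards; if more were made, it rises by one per extra call.
- **The text is in the past tense, so a rule change may come too late.** If so, disclosure is what remains.

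**Conclusion.** The concern holds. The only numeric PTSD-symptom trigger cannot be met from first-call scores of 29–35, and from 28 it is met only at the maximum. This follows from the stated item count, rating range and reference score, and needs no distributional assumption. These women were not unmonitored, but no other safeguard gives an action level for PTSD symptoms. How many started in this band, and how many of those worsened, cannot be found in the document. The primary PCL-5 analysis is unaffected. The sponsor should correct or disclose this: it is a safety rule that fails for the most severe starters, and the remedy is small.

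**What to change.** In Participant safeguards, state the trigger as follows:

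> A rise of 7 or more points from the first-call score, or a total of 35 reached from a lower first-call score. For a first-call score of 35, worsening reported by the participant since that call prompts the same coach discussion, with investigator discussion if it appears study-related.

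The clinical team may prefer a cut below 35, which would also catch moves such as 29 to 34.

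The cost is one sentence and some extra coach discussions, confined to women who start at 29–35 and held within scheduled calls. Some will follow chance rises. Their number cannot be computed, because the document gives no test-retest figure for the seven-item form; the r = .84 under Primary outcome is for the 20-item PCL-5.

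If monitoring has ended, replace the rule change with one sentence in the same section stating that the numeric trigger did not reach first-call scores of 29–35. This adds no participant contact, and it helps anyone who interprets how often the trigger fired or who reuses the safeguard.
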